10.7. COVID-19 Impact

COVID-19 impact will not be analyzed for the CSR.

This document is confidential.

11. Conventions

11.1. Derived Dates

Derived dates for defining analysis periods are defined as follows:

- Study drug start date: Date of first dose of study drug from Study Drug Accountability CRF.
- Imputed study medication stop date: If the study medication stop date is (1) non-complete or (2) complete but before the study medication start date, then the imputed stop date is set to the study medication start date. Otherwise, the imputed stop date is set to the complete study medication stop date. Derived only for subject dosing diary records with complete study medication start date and number of capsules taken ≥ 0.
- Study drug end date: Latest of (1) complete study medication start dates and (2) imputed study medication stop dates. Both (1) and (2) are from subject dosing diary records with number of capsules taken > 0.
- Study drug last date: Study drug end date derived only for subjects with non-missing response to the question “Did the subject complete the study (including the follow-up visit)?” on the Subject Disposition CRF. Thus, in an interim analysis, all post-baseline data are included for a subject who is still on study. At the last database lock, the study drug last date is equal to the study drug end date.
- COVID-19 visit date: (1) Complete visit date, if it exists; (2) otherwise, complete date the visit was planned to occur for a missed visit.
- Last contact date: (1) Earliest complete death date from the AE CRF, if it exists; (2) otherwise, the latest complete date of the following: AE start or stop; COVID-19 visit for in-person or remote visits; ECG; informed consent; laboratory test collection; non-study medication start or stop; physical exam; physical measurement; procedure; questionnaire; study medication start or stop; vital sign; visit. If the last contact date is after the most recent raw database creation date, then it is set to the most recent raw database creation date.
- Death date: Last contact date derived only for subjects who died (see Section 11.1).

No imputations are performed on these derived dates unless specified otherwise. Complete dates are those with valid, non-missing day, month, and year.

11.2. Analysis Periods

Analysis periods are defined as follows:

- Pre-treatment: measurement date/time on or before the study drug start date. This period is used to derive baseline values and to assess safety endpoints. Note that all measurements are pre-treatment for subjects in the enrolled analysis set with missing study drug start date. Note that AEs with imputed start date equal to the study drug start date are NOT part of this period.
 - Pre-treatment will include Visits 1 – 5 / Study Days -29 – 1
- On-treatment: measurement date/time after the study drug start date through the study drug last date + 7 days or ending at the follow-up visit, whichever is earliest. This period is used to assess safety endpoints on treatment. Note that AEs with imputed start date equal to the study drug start date are part of this period.

This document is confidential.

- On-treatment will include Visits 6 – 8 / Study Days 1 – 28
- Follow-up: measurement date after the study drug last date + 7 days or starting at the follow-up visit, whichever is earliest. This period is used to assess safety endpoints during follow-up.
 - Follow-up will include Visit 9 / Study Days 35 – 41

See [Section 11.1](#) for derived dates for determining analysis periods. If measurement time is missing, not collected, or not applicable for a parameter, then the measurement date is compared to the derived date.

This document is confidential.

12. Interim Analyses

No interim analyses are planned for this study.

This document is confidential.

SAP text Version: SAP text version 2.0 24-May-2023

Filing requirements: TMF

Page 36 of 42

13. Changes from Analysis Planned in Protocol

The Treated Population is defined in the study protocol. However, it has been renamed the Safety Population in the SAP.

One additional study populations were added that are not defined in the study protocol, the Follow-up population.

This document is confidential.

14. Quality Control

SAS programs are developed to produce output such as analysis data sets, summary tables, data listings, figures or statistical analyses. An overview of the development of programs is detailed in Syneos Health Developing Statistical Programs SOP (3907) .

Syneos Health Developing Statistical Programs SOP (3907), Conducting the Transfer of Biostatistical Deliverables SOP (3908) and the SAS Programming and Validation Plan describes the quality control procedures that are performed for all SAS programs and output. Quality control is defined here as the operational techniques and activities undertaken to verify that the SAS programs produce the output by checking for their logic, efficiency and commenting and by review of the produced output.

This document is confidential.

SAP text Version: SAP text version 2.0 24-May-2023

Filing requirements: TMF

Page 38 of 42

15. Shells

The TFL shells will be provided as a separate document.

This document is confidential.

SAP text Version: SAP text version 2.0 24-May-2023

Filing requirements: TMF

Page 39 of 42

16. Appendices

This document is confidential.

SAP text Version: SAP text version 2.0 24-May-2023

Filing requirements: TMF

Page 40 of 42

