10.2.2 Part 2 – Dosing/Treatment Period

Visit 5: Onsite Day 1 (predose)

- Review inclusion/exclusion criteria to verify eligibility to enter the dosing period.
Note: If subject does not recover to an FEV₁ within 90% of baseline, additional washout time will be allowed, and the Visit 5 predose procedures may be repeated. If additional retest is required, the screening period may be extended beyond 4 weeks. If these criteria are met, sputum will be induced.
- Vital signs will be recorded.
- Spirometry measurements will be recorded.
- AEs, concomitant medications, and ongoing medications will be recorded.
- Blood samples for hematology and chemistry will be obtained.
- A urine sample for urinalysis will be obtained.
- WOCBP will have a urine pregnancy test performed; a negative result must be obtained before study drug treatment may be administered.
- A methacholine challenge will be performed; sputum will be induced.
- S-STS will be conducted.
- Dispensation of Meal and Daily Study Drug Dosing Diary.

Randomization and first dose: After predose assessments are conducted during Visit 5, subjects will be randomized (per IWRs) to receive zavegeptan or placebo study treatment. Subjects will take their first prescribed dose onsite at the clinic and should continue to take their dose consistently at the same time of day, preferably once in the morning and once in the evening, through Visit 8. Each dose of study drug should be taken while fasting (e.g., at least 1 hour before breakfast/first meal of the day for the first dose, and at least 4 hours after the previous meal for the second dose). Subjects should not consume food other than water for 1 hour after dosing.

3-Day Allergen Triad

Visit 6: Onsite (pre-allergen challenge)

- Subjects will be asked to provide the time of their evening dose and meal on evening before this visit.
- After having fasted overnight; a blood sample for PK measurement will be collected for zavegeptan concentration measurement (predose). Subjects will take the morning dose onsite at the clinic and should not consume food other than water for 1 hour after dose. Exact time of dosing and PK sample collection will be documented. Study procedures may begin immediately after dosing.
- Vital signs will be recorded.
- Spirometry measurements will be recorded.

- AEs, concomitant medications, and ongoing medications will be recorded.
- A methacholine challenge will be conducted; sputum will be induced postdose.

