15.3 Safety Analysis

All reported AEs will be coded using the Medical Dictionary for Regulatory Activities (MedDRA) latest version available at start of the study. The incidence of treatment-emergent

AEs (TEAEs; events with onset dates on or after the start of the study drug) will be included in incidence tables. Events with missing onset dates will be included as treatment-emergent. If a subject experiences more than 1 occurrence of the same AE, the occurrence with the greatest severity and the closest association with the study drug will be used in the summary tables. Treatment-related AEs, SAEs and AEs causing discontinuation will be tabulated. All AEs will be listed by subject, along with information regarding onset, duration, relationship and severity to study drug, action taken with study drug, treatment of event, and outcome.

Clinically significant laboratory test abnormalities will be identified as Grade 3 to 4 laboratory test results graded according to numeric laboratory test criteria in Common Terminology Criteria for Adverse Events (CTCAE) version 5.0 (2017), if available. Otherwise, if CTCAE grades are not available, then results will be graded according to numeric laboratory test criteria in Division of Aids (DAIDS) Table for Grading the Severity of Adult and Pediatric AEs. If a participant has a laboratory test abnormality with different toxicity grades over time, then only the highest toxicity grade will be reported in the lab abnormality summary table.

Clinical laboratory data and vital signs will be summarized using descriptive statistics, including mean values and mean change from baseline values, as well as numbers of subjects with values outside limits of the normal range at each time point.

Summary tables will be provided for concomitant medications initiated during the study period.

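### AEs dated Day 1 are counted as on-treatment by calendar date, so a recorded reaction to the Visit 5 predose methacholine challenge or sputum induction enters the TEAE counts although it began before randomisation and first dose

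*SAP*

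**What the plan says.** SAP 11.2 (Analysis Periods) settles AEs that start on the day of first dose in two places. Under pre-treatment it says: "Note that AEs with imputed start date equal to the study drug start date are NOT part of this period". Under on-treatment it says: "Note that AEs with imputed start date equal to the study drug start date are part of this period". The anchor, defined in SAP 11.1, is a calendar date: "Date of first dose of study drug from Study Drug Accountability CRF". Protocol 15.3 agrees, describing TEAEs as "events with onset dates on or after the start of the study drug".

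The order of events on Day 1 is in Protocol 10.2.2. Among the Visit 5 predose procedures is: "A methacholine challenge will be performed; sputum will be induced". Only then does treatment start: "After predose assessments are conducted during Visit 5, subjects will be randomized", with the first dose taken at the clinic. Protocol 7.1 gives the same order. Table 10-1 has AEs recorded at Visit 5, and Protocol 12.1 collects them from informed consent.

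TEAE frequency is a secondary endpoint (Protocol 6.2.2). SAP 10.1.3 tabulates on-treatment AEs by intensity and by relationship to study drug.

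**The concern.** A Day 1 AE rule based on date alone matters little when nothing provocative happens before the first dose. Here the visit begins with a bronchial provocation test that runs until FEV1 has fallen by at least 20% (Protocol 11.1.1), followed by sputum induction. Cough, wheeze or chest tightness at that point precedes both randomisation and dosing and cannot be an effect of zavegepant or placebo. If a site records it as an AE, the stated rule still counts it as on-treatment.

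At stake is how well the TEAE table describes what happened under treatment. Events unrelated to treatment assignment raise the incidence in both arms and blur any real difference. In arms of about a dozen subjects, a few of them can also fall unevenly by chance.

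**Working it through.** **Tracing the rule.** The plan gives no figure on this point, so the first check is to follow one event through the text.

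1. A symptom starts after the Visit 5 challenge and before randomisation, and is recorded as an AE.
2. Its start date equals the study drug start date, because the first dose is taken at the same visit.
3. SAP 11.2 excludes it from pre-treatment and includes it in on-treatment. Protocol 15.3 also makes it a TEAE.
4. It is tabulated under the subject's arm in the safety analysis set.

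SAP 11.2 is otherwise written in terms of date and time, falling back on date alone only where needed: "If measurement time is missing, not collected, or not applicable for a parameter, then the measurement date is compared to the derived date". The two AE notes override this for Day 1. Other Day 1 measurements go the opposite way, since those on or before the start date are pre-treatment. Neither document provides a predose flag for AEs.

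**Size.** Inputs from the documents: 24 planned subjects, 12 per arm (Protocol 15.1). Assumed inputs, since the documents give none:
- q, the probability of a recorded predose Day 1 reaction, is 2% to 30%. It is the same in both arms because the event precedes randomisation.
- t, the true on-treatment incidence, is 30% in both arms for the inflation example, and 50% versus 25% for the dilution example.
- Reactions are independent of later events.

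Formulas:
- Expected subjects with a predose reaction = 24q
- P(at least one among 24) = 1 − (1 − q)^24
- Reported incidence = 1 − (1 − t)(1 − q) = t + q(1 − t)
- Reported difference = (t₁ − t₂)(1 − q)

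| q (assumed) | 24q | P(at least one) | Reported incidence, true 30% | Reported difference, true 25 points |
|---|---|---|---|---|
| 2% | 0.5 | 38% | 31.4% | 24.5 points |
| 10% | 2.4 | 92% | 37.0% | 22.5 points |
| 30% | 7.2 | about 100% | 51.0% | 17.5 points |

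Example for q = 10%: 1 − 0.70 × 0.90 = 37.0%, and 25 × 0.90 = 22.5 points.

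The net gain in subjects counted per arm is 12q(1 − t), because a subject who has another TEAE is already counted. At t = 30% this is 0.17, 0.84 and 2.52 subjects for q = 2%, 10% and 30%.

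**Chance imbalance.** With X and Y independent Binomial(12, q), the probability that the arms differ by two or more subjects with a predose reaction is 14% at q = 5%, 29% at 10%, 44% at 20% and 50% at 30%. These count reactions, not net additions to TEAE incidence. One subject is 1/12 = 8.3 percentage points of a planned arm.

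**The case against.** The strongest reply is that assigning all of Day 1 to treatment is a deliberate, cautious convention, shared by both documents, which ensures that no postdose event is lost. That stands where onset time is unknown. It gives no reason to count an event documented to precede the first dose.

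Two further replies concern wording. The SAP speaks of an imputed start date, and AE date imputation is left to the Core SAP, which is not among the documents. But in SAP 11.1 the comparable imputed stop date equals the actual date when that is complete and not before the start date, and Protocol 15.3 reaches the same result without the word imputed. Protocol 12.3 treats pre-existing conditions up to first dosing as concomitant, yet has illnesses first occurring during the study documented as AEs, so it does not clearly remove a new procedure reaction.

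Other points do limit the concern:
- The FEV1 fall is the test's intended endpoint and need not be recorded as an AE.
- All subjects undergo further challenges and sputum induction at Visits 6 to 8, so those prone to symptoms may be counted anyway. That overlap would make the inflation smaller than independence implies.
- Safety is summarised as frequencies by treatment group (SAP 4.2), with no planned between-arm AE test.
- SAP section 2 reports that the study stopped early for low enrolment. Actual arm sizes are not given, so calculations at 12 per arm describe the plan, not the data.

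A reader might go further in three ways that the documents do not support:
- **That predose reactions will be reported as drug-related.** Protocol 12.1 requires a causality judgement that considers the temporal sequence from dosing, so they should be classed as unrelated or unlikely related. They still enter the overall on-treatment counts.
- **That an assumed reaction rate times 12 gives the number of false TEAE subjects per arm.** No rate is given, and that product ignores subjects who have another TEAE.
- **That Days 29 to 34 belong to no period.** The SAP does say "On-treatment will include Visits 6 – 8 / Study Days 1 – 28" and labels follow-up as Days 35 to 41. But the operative rule above that label runs to seven days after the last dose or the follow-up visit, whichever comes first. With a last dose on Day 28, an AE on Days 29 to 34 before Visit 9 is on-treatment. The label is loose wording and leaves no data unassigned.

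**Conclusion.** The point holds, at modest severity. Under the stated rule, any reaction recorded as an AE between the start of the Visit 5 procedures and the first dose is counted as treatment-emergent. The consequences are inflated descriptive TEAE incidence in both arms, dilution of a true difference by (1 − q), and possible chance imbalance in small arms.

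The size depends on q, which the documents do not give. At 2% the effect is negligible. At 30% a true 25-point difference would be reported as 17.5. The dilution factor assumes that predose reactions are independent of later events.

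There is no systematic bias towards either arm, because these events precede randomisation and are balanced in expectation. The LAR endpoint, its sample size and its power are untouched.

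**What to change.** In SAP 11.2, add a rule for AEs only. An AE with onset on the study drug start date is pre-treatment if it is documented to have started before the first dose, either by onset time or by a site-confirmed before-first-dose flag. All other AEs with that onset date, including those of unknown time, remain on-treatment. State in SAP section 13 that this departs from the date-only definition in Protocol 15.3.

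The comparison should be feasible: the first dose is taken on site under supervision (Protocol 9.4 and 10.2.2) and the diary captures dosing times (Table 10-1, footnote h). Whether the AE form holds onset time is not stated. If it does not, query sites about Day 1 AEs only.

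If times cannot be recovered, which is possible in a terminated study, flag the Day 1 AEs attributed to the predose procedures and show the on-treatment AE table with and without them.

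The cost is one derivation rule, a few site queries and slightly fewer reported TEAEs. Challenge symptoms that start after the first dose, and those of unknown time, would still count as on-treatment.

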Appendix A Relevant Protocol Deviations

Relevant eligibility protocol deviations include the following categories:

- Respiratory disease other than mild intermittent asthma
- Baseline FEV₁ < 70% of predicted value
- Score on the Sheehan-Suicidality Tracking Scale (S-STS) at screening > 0
- Methacholine challenge (PC₂₀ > 16 mg/mL)
- History of liver disease or viral hepatitis
- History of HIV
- Use of tobacco products and/or vaping products within the previous 12 months or smoking history > 10 pack years.
- Positive drug screen
- Findings out of range, defined any as any of the following subcategories:
 - At any time during the study:
 - Females with a positive pregnancy test
 - During pre-treatment period:
 - ALT \geq 1.5x ULN
 - AST \geq 1.5x ULN
 - Direct bilirubin \geq 1.5x ULN
 - Indirect bilirubin \geq 1.5x ULN
 - Total bilirubin \geq 1.5x ULN
 - BMI \geq 33 kg/m²
 - Estimated glomerular filtration rate (eGFR) according to the re-expressed abbreviated (4-variable) Modification of Diet in Renal Disease (MDRD) Study equation \leq 40 mL/min/1.73m²
 - Systolic blood pressure > 150 mmHg
 - Diastolic blood pressure > 100 mmHg

Relevant subject management protocol deviations include the following categories:

- Study drug dosing
 - < 80% compliance
- Study drug dosing error, defined as any of the following subcategories:
 - Study drug taken but not randomized
 - Study drug actually received different from randomized treatment assignment
- Missed study exit visit
- Missed methacholine challenge, skin allergen challenge, allergen challenge
- Washout period after methacholine challenge and sputum induction on Visit 4 other than 2-4 weeks
- Visit 5 methacholine challenge FEV₁ < 90% of baseline for FEV₁
- Visit 9 (follow up onsite visit) conducted outside 7-10 day after last study treatment window
- Use of any prohibited medications (refer to Table 9.1 in the protocol) on or after informed consent
 - CGRP targeting medications
 - Anti-IgE therapy
 - Allergy immunotherapy
 - Investigational drug
 - Systemic, inhaled, topical nasal steroids
 - Immunosuppressives
 - Anticoagulants
 - Theophylline
 - Nedocromil or cromoglycate
 - Modafinil

This document is confidential.

- St. John's wort
- Atypical antipsychotics such as aripiprazole, olanzapine, quetiapine, risperidone, ziprasidone
- Mood stabilizers such as lithium, lamotrigine or divalproex/valproic acid/valproate
- Strong cytochrome P450 3A4 (CYP3A4) inhibitors or inducers such as clarithromycin, cobicistat, conivaptan, danoprevir and ritonavir, elvitegravir and ritonavir, indinavir and ritonavir, itraconazole, ketoconazole, lopinavir and ritonavir, nefazodone, neflifavir, paritaprevir and ritonavir and (ombitasvir and/or dasabuvir), posaconazole, ritonavir, saquinavir and ritonavir, tipranavir and ritonavir, troleandomycin, voriconazole, apalutamide, carbamazepine, phenobarbital, phenytoin, rifampin, rifapentine, St. John's wort
- Potent P-glycoprotein (P-gp) inhibitors or inducers such as amiodarone, clarithromycin, cyclosporine, dronedarone, itraconazole, lapatinib, propafenone, quinidine, ritonavir, verapamil
- Leukotriene modifiers
- Long-acting beta agonists
- Long-acting anticholinergics
- Antimuscarinics
- Non-steroidal anti-inflammatory drugs

This document is confidential.
